7.2.1. Graded Laboratory Values

The DAIDS Table for Grading the Severity of Adult and Pediatric Adverse Event, Version 2.1 (July 2017) will be used to assign toxicity grades (0 to 4) to laboratory results for analysis. Grade 0 includes all values that do not meet the criteria for an abnormality of at least Grade 1.

7.2.1.1. Treatment-Emergent Laboratory Abnormalities

Treatment-emergent laboratory abnormalities are defined as values that increase at least 1 toxicity grade from baseline at any postbaseline time point, up to and including the date of last dose of study drug plus 30 days participants who permanently discontinued study drug, or the last available date in the database snapshot for participants who were still on treatment at the time of an interim analysis. If the relevant baseline laboratory value is missing, any abnormality of at least Grade 1 observed within the time frame specified above will be considered treatment emergent.

7.2.1.2. Summaries of Laboratory Abnormalities

A by-participant listing of treatment-emergent laboratory abnormalities will be provided by participant ID number and visit in chronological order. This listing will include all test results that were collected throughout the study for the lab test of interest, with all applicable severity grades and abnormal flags displayed.

For INR and aPTT, protocol specified toxicity grading scale depends on the upper limit of normal range (ULN). While the ULN of INR and aPTT depends on whether the participant is taking anticoagulant medication or not (ie, Not taking oral anticoagulant: 0.8 – 1.2; Taking oral anticoagulant: 2.0 – 3.0), this information is not collected by the reference laboratory. As a result, INR and aPTT will be graded by assuming participant is not taking an oral anticoagulant, which is a conservative approach that may lead to over-reporting of abnormalities for INR and aPTT.

7.2.2. Liver-related Laboratory Evaluations

Liver-related abnormalities after initial study drug dosing will be examined using the participants who were reported to have the following laboratory test values for postbaseline measurements:

- AST: (a) > 3 times of the upper limit of reference range (ULN); (b) > 5 x ULN; (c) > 10 x ULN; (d) > 20 x ULN
- ALT: (a) > 3 x ULN; (b) > 5 x ULN; (c) > 10 x ULN; (d) > 20 x ULN
- AST or ALT: (a) > 3 x ULN; (b) > 5 x ULN; (c) > 10 x ULN; (d) > 20 x ULN
- Total bilirubin > 2 x ULN
- ALP > 1.5 x ULN
- AST or ALT > 3 x ULN and total bilirubin: (a) > 1.5 x ULN; (b) > 2 x ULN

A listing of participants who met at least 1 of the above criteria will be provided.

7.3. Body Weight and Vital Signs

A by-participant listing of vital signs will be provided by participant ID number and visit in chronological order. Body weight, height, and BMI will be included in the vital signs listing, if space permits. If not, they will be provided separately.

7.4. Prior and Concomitant Medications

Medications collected at screening and during the study will be coded using the current version of the Gilead-modified World Health Organization (WHO) Drug dictionary.

Prior medications are defined as any medications with a start date prior to the first dosing date of study drug, regardless of when the stop date is. If a partial start date is entered, the medication will be considered prior unless the month and year (if day is missing) or year (if day and month are missing) of the start date are after the first dosing date. Medications with a completely missing start date will be considered as prior medications.

Concomitant medications are defined as medications taken while a participant took study drug.

All prior and concomitant medications (other than per-protocol study drugs) will be provided in a by-participant listing sorted by participant ID number and administration date in chronological order. This listing will include Anatomical Therapeutic Chemical (ATC) drug class Level 2.

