1.1. Study Objectives and Endpoints

Primary Objective(s)	Primary Endpoint(s)

To evaluate the plasma pharmacokinetics (PK) of ODV in pediatric participants with COVID-19To evaluate the safety and tolerability of ODV in pediatric participants with COVID-19	
PK parameters (AUC_{0-12}, C_{max}, and C_{trough}) for ODV metabolite, GS-441524Incidence of treatment-emergent adverse events (AEs) by Day 35Incidence of treatment-emergent laboratory abnormalities by Day 35
Secondary Objective(s)	Secondary Endpoint(s)

To assess the impact of ODV on time to sustained alleviation of targeted COVID-19 symptoms in pediatric participants with COVID-19To evaluate the antiviral activity of ODV on SARS-CoV-2 nasal swab viral load in pediatric participants with COVID-19To assess the impact of ODV on the requirement for supplemental oxygen in pediatric participants with COVID 19To evaluate palatability and acceptability of ODV in pediatric participants with COVID-19	
Time to sustained alleviation of targeted COVID-19 symptoms by Day 35Change from baseline in SARS-CoV-2 nasal swab viral load at Day 5Proportion of participants who require supplemental oxygen support (low flow oxygen, high flow oxygen, noninvasive ventilation, mechanical ventilation, or extracorporeal membrane oxygenation) by Day 35Assessment of palatability and acceptability scores of each formulation at Day 5

• To provide data on the use of medications other than remdesivir (RDV) and ODV for treatment of COVID-19 in pediatric participants with COVID-19• To assess the impact of ODV on COVID-19-related hospitalizations or all-cause death in pediatric participants with COVID-19	
• Proportion of participants with concomitant use of medications other than RDV and ODV for treatment of COVID-19 by Day 35• Proportion of participants with COVID-19-related hospitalization or all-cause death by Day 35
---	---

CCI

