1.2. Study Design

This is a Phase 2/3, single-arm, multi-cohort, open-label study to evaluate the safety, PK, and efficacy of ODV in pediatric participants with COVID-19 who are at risk of progression to severe disease.

At least 52 participants aged 0 days to < 18 years were planned to be enrolled as described in [Table 1-1](#). Participants were enrolled in a staggered manner and received treatment with ODV. Cohorts were opened for enrollment based upon availability of a suitable pediatric formulation and availability of preliminary safety and PK data.

Table 1-1. Study Design

Cohort	Description	Dose	Number of participants
Pediatric participants ≥ 28 days to < 18 years old			
1	≥ 6 years to < 18 years and weight ≥ 40 kg	ODV CCI administered orally BID for 5 days	12
2	≥ 6 years to < 18 years and weight ≥ 20 kg to < 40 kg	ODV CCI administered orally BID for 5 days	12
3	≥ 2 years to < 18 years and weight ≥ 12 kg to < 20 kg	TBC	12
4	≥ 28 days to < 18 years and weight ≥ 3 kg to < 12 kg	TBC	12
Term neonatal participants 0 days to < 28 days old			
5	≥ 14 days to < 28 days of age, GA ≥ 37 weeks and weight ≥ 2.5 kg	TBC	≥ 4
6	0 days to < 14 days of age, GA ≥ 37 weeks and birth weight ≥ 2.5 kg	TBC	All available
Preterm neonates and infants 0 days to < 56 days old			
7	0 days to < 56 days of age, GA < 37 weeks and birth weight ≥ 1.5 kg	TBC	All available

GA = gestational age; TBC = To be confirmed.

Participants had to have:

- SARS-CoV-2 infection confirmed by polymerase chain reaction or an alternative molecular diagnostic assay
- Initial onset of COVID-19 signs/symptoms ≤ 5 days before screening with ≥ 1 sign/symptom
- Presence of ≥ 1 characteristic or underlying medical condition associated with an increased risk of developing severe illness due to COVID-19

Randomization and treatment codes were not applicable in this study. Blinding of treatment assignments or data was not applicable in this study.

The study treatment period was 5 days with a posttreatment follow-up period of 30 days after the last dose of study drug.

The schedule of study procedures is presented in [Appendix 1](#).

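### SAP Section 7.4 ties concomitant medication to the dosing days, so a dated medicine started after the last dose is left out of the only visible listing that can support a Day 35 endpoint

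*SAP*

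**What the plan says.** Section 1.1 includes this secondary endpoint: "Proportion of participants with concomitant use of medications other than RDV and ODV for treatment of COVID-19 by Day 35". Section 1.2 gives the time frame: "The study treatment period was 5 days with a posttreatment follow-up period of 30 days after the last dose of study drug".

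Section 7.4 first covers medication data from the whole study: "Medications collected at screening and during the study will be coded". It then sets up two classes. One is prior: "Prior medications are defined as any medications with a start date prior to the first dosing date of study drug", whatever the stop date. The other is concomitant: "Concomitant medications are defined as medications taken while a participant took study drug". There is no class for medicines begun after dosing ends. The output is then specified as: "All prior and concomitant medications (other than per-protocol study drugs) will be provided in a by-participant listing".

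Incomplete start dates have their own rules. For partial dates: "If a partial start date is entered, the medication will be considered prior unless the month and year" (or the year alone, if that is all that is known) falls after the first dosing date. For absent dates: "Medications with a completely missing start date will be considered as prior medications".

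Sections 3, 6.4 and 7.8 say that, after early termination, no tables or figures will be produced and only by-participant listings will be given. The visible items in Section 6.2 are symptoms, viral load, oxygen supplementation and hospitalization; none concerns medication.

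**The concern.** The word concomitant covers about five or six days in Section 7.4 and 35 days in the Section 1.1 endpoint. A programmer who follows Section 7.4 exactly would code every medicine collected during the study and then leave out of the listing any well-dated medicine first taken after the last dose.

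With few participants and no tables, a reader of the study report must set each child's listings side by side. Viral-load visit windows run to Day 35 (Table 3-4), the symptom and hospitalization endpoints run to Day 35, and treatment-emergent adverse events run to 30 days after study drug is stopped (Section 7.1.5.1). The medication record alone would admit no new medicine after the last dose. If a child began another COVID-19 medicine in follow-up, the later records would be read without it. With so few children, one omission can change how a case is understood.

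**Working it through.** **Inputs**

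- Endpoint horizon: Day 35 (Section 1.1).
- Treatment 5 days, follow-up 30 days after the last dose (Section 1.2).
- Last dosing day, L: Day 5 under the planned course. Day 6 is the latest day to which a missing last dosing date may be imputed (Section 4.2).
- Class definitions and listing content: Section 7.4.

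**Step 1. Reproduce the horizon.** 5 + 30 = 35, which matches the plan. With a last dose on Day 6, follow-up ends on 6 + 30 = Day 36.

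**Step 2. Endpoint days outside the concomitant definition.** I read the definition as running from the first to the last dosing day, inclusive. Days outside = 35 − L.

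- L = 5: 35 − 5 = 30 days; 30/35 = 85.7%.
- L = 6: 35 − 6 = 29 days; 29/35 = 82.9%.

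A child who stops study drug early has a smaller L and so more days outside.

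**Step 3. Classify medicines with complete dates.** Prior: start before Day 1. Concomitant: start on or before Day L and stop on or after Day 1.

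| Taken on study days | Last dose Day 5 | Last dose Day 6 |
|---|---|---|
| −3 to −1 | prior | prior |
| −3 to 10 | prior and concomitant | prior and concomitant |
| 2 to 4 | concomitant | concomitant |
| 5 to 9 | concomitant | concomitant |
| 6 to 9 | neither | concomitant |
| 7 to 12 | neither | neither |
| 10 to 14 | neither | neither |
| 30 to 35 | neither | neither |

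Anything marked neither is outside the specified listing, although its use falls within the endpoint window. A medicine begun before or during dosing is listed even if it continues well beyond the last dose; the gap concerns start dates only.

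**Step 4. Incomplete start dates.** A medicine begun after the last dose with no start date at all is classed as prior and so is listed. So is one with the day missing, if the recorded month is the month of first dose. One with the day missing and a later recorded month is not prior; if it began after the last dose, it is not concomitant either, and it drops out. The date rules therefore keep some poorly dated medicines, under the wrong label, while the fully dated ones are lost.

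**The case against.** The best defence is that nothing is estimated. No proportion will be calculated for this endpoint and no test is planned (Sections 3, 3.5 and 6.4). A reader might infer that users of other COVID-19 treatment will be undercounted; the plan makes no such count, so that reading is not supported. This stands and limits the point to the completeness of a listing.

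Other parts also stand:

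- A reader might take 86% or 83% as the share of medicines missed. These are shares of calendar days. The documents give no distribution of start days, and the number of medicines affected could be zero.
- It is tempting to say that every medicine begun after dosing is lost. The rules for incomplete dates keep some of them.
- It is tempting to call the Section 7.4 listing the endpoint's only output. Part of Section 6 is redacted, so another listing cannot be excluded. Only visible output is as far as the text goes.
- A reader might infer that the viral-load endpoint is confounded. It is a change from baseline at Day 5, and the Day 5 window in Table 3-4 covers Days 5 to 6, so a medicine begun after the last dose leaves it essentially untouched. Only later records are exposed.

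The defence can also say that the intent is broader, since Section 7.4 opens with medications collected during the study and the schedule in Appendix 1 uses concomitant medications as its general heading for data collection. That suggests loose wording and not a decision to drop follow-up data, but the listing is specified through the narrow definition. A programmer who lists everything departs from the written rule. The hospitalization, oxygen and adverse-event listings would still show worsening, but as specified they are not medication listings.

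**Conclusion.** The point holds as a defect in a stated rule. Read literally, Section 7.4 omits any medicine with a complete start date after the last dose, and no visible text supplies another medication listing for the Day 35 endpoint. The definition leaves out start dates on 30 of the 35 endpoint days with a last dose on Day 5, or 29 with a last dose on Day 6. The consequence is an incomplete by-participant listing, with viral-load, symptom, hospitalization and adverse-event records after Day 5 or 6 read without knowledge of added treatment. It is not a biased estimate.

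This rests on two assumptions: that the definition means first to last dosing day inclusive, and that the redacted text holds no further medication listing. Severity is minor to moderate. It should be corrected because the correction is cheap, but it does not undermine any planned estimate.

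**What to change.** Amend Section 7.4 so that the listing contains prior medications and all medications taken from the first dosing date through the Last Study Date, which Section 3.8.1 already defines. Add a column showing whether each medicine started before the first dose, on treatment or after the last dose, and a column for the study day of start. The study day matters because the final visit has a window of ±5 days (Appendix 1), so the Last Study Date can fall on either side of Day 35; with it, use by Day 35 can be read off directly. Where the start date is incomplete, show it as recorded, so that a medicine classed as prior by default can be recognised.

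Where the eCRF records indication, flag medicines other than remdesivir and obeldesivir given for COVID-19. The SAP does not show whether that field exists, so this flag is conditional.

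The cost is a revised sentence, two derived columns and possibly a flag. Section 7.4 indicates that the medications are already collected and coded, so the listing change needs no new medication records. The listing may become slightly longer.

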7.5. Tanner Stage Assessment

Tanner Stage results at Day 1 and during the study, if available, will be listed.

7.6. Palatability and Acceptability Assessment

Palatability and acceptability assessments will be listed.

7.7. Other Safety Measures

A by-participant listing of participant pregnancies during the study will be provided by participant ID number (in ascending order).

7.8. Changes From Protocol-Specified Safety Analyses

This study was terminated early; hence the protocol-specified safety analyses will not be provided. Only by-participant listings will be presented.

8. PHARMACOKINETIC (PK) ANALYSES

8.1. PK Sample Collection

A single PK blood sample was planned to be collected at the following times and visits:

- Cohorts 1 and 2:

- Days 3: 1 sample between CCI [REDACTED]
- Day 5: predose CCI [REDACTED] and at CCI [REDACTED] CCI [REDACTED]
[REDACTED] postdose
- Day 5: CCI [REDACTED] postdose for hospitalized participants only

As many of the above specified PK samples should have been obtained from each participant as was feasible.

8.2. PK Analyses Related to Sparse PK Sampling

The following listings will be provided:

- PK sampling details by participant, including procedures, differences in scheduled and actual draw times, and sample age from the PK samples as well as concentration data.

8.3. Changes From Protocol-Specified PK Analyses

This study was terminated early; hence the protocol-specified PK analyses will not be provided. Only by-participant listings will be presented.

10. SOFTWARE

SAS® Software Version 9.4. SAS Institute Inc., Cary, NC, USA.

11. SAP REVISION

Revision Date (DD MMM YYYY)	Section	Summary of Revision	Reason for Revision

Appendix 1. Schedule of Assessments

	Screening/ (D -1) ^a	Baseline/ D 1 ^a	D 3	D 5	D 8	D 14	D 21	D 28	EOS/ D 35
	-	-	-	-	± 1 d	± 2 d	± 2 d	± 2 d	± 5 d
	In person		In person or remote ^b	In person	In person or remote ^b		Virtual ^c		In person
Participant and/or parent or legal guardian consent/assent									
Medical history ^d									
Document SARS-CoV-2 infection									
Complete physical examination ^e									
Symptom-directed physical examination ^e									
Body weight									
Height/length ^f									
Last recorded Apgar score if < 24 hours of age									
Birth weight if < 56 days of age									
Gestational age if < 1 years of age									
Vital signs ^g									
Tanner stage assessment if ≥ 6 years of age									
Hematology, chemistry									
Urinalysis									
Routine coagulation test (PT/aPTT with calculated INR)									
Neonatal bilirubin panel for all neonates < 14 days, and any neonate presenting with jaundice									
Urine pregnancy test ^h									
Midturbinate nasal swab ⁱ									
Review inclusion/exclusion criteria									
Participant and/or caregiver symptom assessment ^j									
PK sample ^k									
Study drug dispensation									
Study drug administration ^l									
Study drug return ^m									
Concomitant medications									
Hospitalization details ⁿ									
Oxygen supplementation requirement ^o									

CCI

	Screening/ (D -1) ^a	Baseline/ D 1 ^a	D 3	D 5	D 8	D 14	D 21	D 28	EOS/ D 35		
	-	-	-	-	± 1 d	± 2 d	± 2 d	± 2 d	± 5 d		
	In person		In person or remote ^b	In person	In person or remote ^b	Virtual ^c		In person			
Adverse events ^d	CCI										
Acceptability/palatability assessment											

aPTT = activated partial thromboplastin time; COVID-19 = coronavirus disease 2019; D/d = day; EOS = end of study; Ig = immunoglobulin; INR = international normalized ratio; MAP = mean arterial pressure; PT = prothrombin time; PK = pharmacokinetic(s); RT-qPCR = reverse transcription-quantitative polymerase chain reaction; SARS-CoV-2 = severe acute respiratory syndrome coronavirus 2

- a Screening window is within 48 hours of the baseline visit. Baseline visit may occur on the same day as screening. If the Day 1 and Screening visits occur within the same calendar day, do not repeat assessments common to Screening and Day 1 visits.
- b An in-person visit will occur either at a medical facility or as a remote visit at home by a health care professional (where permitted).
- c Virtual visit is defined as an interaction with a health care professional using telephone or online based interaction (eg, telehealth, webcast, videoconferencing).
- d Medical history will include the date of first COVID-19 symptoms, overall COVID-19 symptoms, all COVID-19 vaccinations prior to screening, demographics, baseline characteristics, allergies, and all other medical history.
- e A complete physical examination includes source documentation of general appearance and the following body systems: head, neck, and thyroid; eyes, ears, nose, throat, mouth, and tongue; chest (excluding breasts); respiratory, cardiovascular, lymph nodes, abdomen; skin, hair, nails; musculoskeletal; and neurological. Urogenital and reproductive examination should only be completed if clinically indicated. A physical examination will only be conducted during an in-person visit by a qualified health care professional.
- f Record length and head circumference if < 28 days at enrollment.
- g Vital signs include heart rate, temperature, blood pressure (MAP if available, systolic and diastolic), respiratory rate, and oxygen saturation. Vital signs will be collected at in-person visits only.
- h For female participants of childbearing potential only.
- i The nasal swab sample will be used for SARS-CoV-2 RT-qPCR, potential infectious viral titer assessment, potential resistance testing, and viral coinfection.
- j Participant and/or caregiver symptom assessment will be completed on stipulated days via a questionnaire (Protocol Section 6.3.7).
- k Refer to Protocol Section 6.3.5 for PK samples collection timepoints. PK samples will be collected on CCI for Cohorts 1 and 2.
- l Study drug administration time will be recorded by investigational site personnel or by participant/parent/caregiver via a diary. Participant to withhold their dose prior to arriving to the site on Day 5, as the dose will be administered at the site.
- m Study drug bottle should be returned by the participant on Day 5, if the participant has already completed both doses of study drug. If the participant has the last dose of study drug remaining by the conclusion of the Day 5 in-person visit, the participant may return the study drug bottle if an in-person visit is conducted on any subsequent visits (including EoS visit). Alternatively, the participant may courier the study drug bottle to the site.
- n To be collected for hospitalized participants. Information to be collected: hospitalization date, reason for hospitalization, discharge date, and discharge outcome.
- o To be collected for hospitalized participants. Refer to Protocol Section 6.3.4 for information collection on oxygen supplementation or oxygenation.
- p All participants presenting with multisystem inflammatory syndrome in children (MIS-C; <https://emergency.cdc.gov/han/2020/han00432.asp>) should be monitored and treated as clinically indicated.
- q To be collected for hospitalization participants.

Appendix 2. Programming Specifications

- 1) If “Age at Day 1” on the Demographics eCRF is not available, age [in years] will be calculated as follows:
 - a) Only year is provided for the date of birth (DOB). Use July 1 for the month and day.
 - i) AGE [in years] is calculated from the number of days between the DOB and Study Day 1,
 - ii) Use the SAS INTCK function to determine the number of “1st-of-month days” (for eg, January 1st, February 1st, March 1st) between DOB and Day 1 (inclusive),
 - iii) Divide the result in (ii) by 12,

AGE = the integer of the result in (iii).

Age for laboratory test reference range will be based on the age at the sample collection date.

- 2) All screened participants refer to all participants who are screened (ie, with nonmissing screening date) and have a screening number. For summaries the same participant is counted only once.
- 3) Screen failure participants are the participants who either:
 - were screened and answered “No” for any inclusion criteria or “Yes” for any exclusion criteria regardless of which version of protocol the participant was consented
 - met all inclusion and exclusion criteria but were not enrolled.
- 4) Participants in the All Enrolled Analysis Set are defined as participants enrolled into the study. IXRSRND is the source to determine whether the participant is enrolled (ie, participant with nonmissing ENRDTN in the IXRSRND dataset), and confirmed by information recorded on the ENROLL eCRF (ie, ENROLLYN = “Yes” in ENROLL dataset).
- 5) Enrolled treatment (ie, TRT01P in ADSL) is derived from IXRSRND, while actual treatment received (ie, TRT01A in ADSL) is assigned as the enrolled treatment if a participant took at least 1 dose of study drug. TRT01A is assigned as blank if the participant was never dosed.
- 6) Body mass index (BMI) will be calculated only at baseline as follows:
 - $BMI = (\text{weight [kg]}) / (\text{height [meters]}^2)$

Baseline height and weight will be used for this calculation if available.

7) BMI-for-age percentile:

- a) Participants < 24 months: BMI-for-age percentile will be computed using WHO SAS package: www.who.int/toolkits/child-growth-standards/software
- b) Participants \geq 2 years to < 20 years will be computed based on CDC: www.cdc.gov/nccdphp/dnpao/growthcharts/resources/sas.htm

8) Risk factors defined in the inclusion criteria:

— Information on following risk factors is collected on the Medical History eCRF:

- CCI [REDACTED]

9) TEAE

Events with Missing Onset Day and/or Month

An event is considered TE if all of the following 3 criteria are met:

- a) The month and year (or year) of onset date is the same as or after the month and year (or year) of the first dose of study drug administration, and
- b) The month and year (or year) of the onset date is the same as or before the month and year (or year) of the 30th day after the date of the last dose of study drug administration, and
- c) End date is as follows:
 - i) The (complete) end date is on or after the first dose date, or
 - ii) The month and year (or year) of end date is the same as or after the month and year (or year) of the first dose of study drug, or
 - iii) End date is completely missing

Events with Completely Missing Onset Date

An AE with a completely missing onset date is defined as TEAE if end date meets any of the 3 criteria specified above.

- 10) The precision in reporting numerical values should be as follows:
 - a) Raw measurements will be reported the same as the data captured electronically or on the eCRF for all but hematology and chemistry values.
 - b) SD and SE will be reported to one more significant decimal place than the raw measurement.
 - c) Mean, median, minimum, Q1, Q3, and maximum will be reported to the same number of decimal places of the raw measurements.

Exceptions may be considered; for eg, if more than 4 significant digits are provided for the measurement.

Precision for derived parameters as follows:

Parameters	Decimal Places
BMI	2
PK concentration	2

- 11) Incomplete death dates will be imputed as the maximum of the study drug start dates, study drug end dates, clinic or virtual visit dates (LSTSVDT), laboratory visit dates (LSTLBDT), COVID-19 symptom assessment questionnaire dates plus 1.

- 12) Graded Laboratory Abnormalities Summary

The following labels will be used for laboratory abnormalities listings:

Category	Lab Test Label Used in I-lbtox Listing	Toxicity Direction	Lab Test Label Used in t-lbtox Table
Hematology	Hemoglobin	Decrease	Hemoglobin (Decreased)
	Lymphocytes	Decrease	Lymphocytes (Decreased)
	Neutrophils	Decrease	Neutrophils (Decreased)
	Platelets	Decrease	Platelets (Decreased)
	WBC	Decrease	WBC (Decreased)
Chemistry	Albumin	Decrease	Albumin (Decreased)
	Alkaline Phosphatase	Increase	Alkaline Phosphatase (Increased)
	ALT	Increase	ALT (Increased)
	AST	Increase	AST (Increased)
	Bicarbonate	Decrease	Bicarbonate (Decreased)
	Corrected Calcium	Increase	Corrected Calcium (Hypercalcemia)
	Corrected Calcium	Decrease	Corrected Calcium (Hypocalcemia)
	Creatine Kinase (CK)	Increase	Creatine Kinase (Increased)
	Creatinine	Increase	Creatinine (Increased)
	Creatinine Clearance	Decrease	Creatinine Clearance by Cockcroft-Gault, Gilead Calculated (Decreased)
	Lipase	Increase	Lipase (Increased)
	Magnesium	Decrease	Magnesium (Hypomagnesemia)
	Phosphate	Decrease	Phosphate (Hypophosphatemia)
	Serum Glucose	Increase	Serum Glucose (Hyperglycemia)
	Serum Glucose	Decrease	Serum Glucose (Hypoglycemia)
	Serum Potassium	Increase	Serum Potassium (Hyperkalemia)
	Serum Potassium	Decrease	Serum Potassium (Hypokalemia)
	Serum Sodium	Increase	Serum Sodium (Hypernatremia)
	Serum Sodium	Decrease	Serum Sodium (Hyponatremia)
	Total Bilirubin	Increase	Total Bilirubin (Hyperbilirubinemia)
	Uric Acid	Increase	Uric Acid (Hyperuricemia)
Coagulation	Activated partial thromboplastin time (aPTT)	Increase	Activated Partial Thromboplastin Time (Increased)
	Prothrombin Intl. Normalized Ratio (INR)	Increase	Prothrombin Intl. Normalized Ratio (Increased)
	Prothrombin Time	Increase	Not Applicable

Refer to item 13 below for more information on glucose.

13) Glucose

Fasting is not required per protocol for collecting glucose sample. Mixed fasting glucose and nonfasting glucose results are presented in the dataset. Fasting glucose or nonfasting Glucose is graded per DAIDS grading scale. The treatment-emergent glucose abnormality will be determined per Section [7.2.1](#) without regard to fasting status (hyperglycemia or hypoglycemia).

GS-US-611-6464-Final-Analysis-SAP-v1.0

ELECTRONIC SIGNATURES

Signed by	Meaning of Signature	Server Date (dd-MMM-yyyy hh:mm:ss)
PPD	Biostatistics eSigned	PPD
PPD	Clinical Pharmacology eSigned	
PPD	Global Development Lead (GDL) eSigned
